**Exclusion criteria**

Participant who meet **ANY** of the following criteria are **NOT** eligible for the Booster Phase:

- B1. Clinically significant infection or other acute illness, including fever  $\geq$  38°C within 48 hours prior to the planned Booster vaccination.
- B2. Participant has an acute or recent infection not due to SARS-CoV-2 and is not symptom-free in the week prior to the Booster vaccination (Visit 7).
- B3. Participant has received any vaccine within 30 days prior Visit 7, with the exception of the seasonal influenza vaccination. Participants will be encouraged to receive this vaccination at least 7 days after their Booster vaccine.
- B4. Participant has abnormal findings in any required study investigations (including medical history, physical examination, and clinical laboratory) that is considered clinically relevant by the Investigator.

iii Participants are considered generally healthy if they have (1) no active disease (acute illness, exacerbation of a chronic condition or a chronic – progressive illness) which requires treatment and/or follow-up, and (2) no disease that is identified as an exclusion criterion or (3) if they are healthy and have a preexisting stable disease, defined as disease not requiring significant change in therapy or hospitalization for worsening disease during the 6 weeks before screening/ before Day 208.

- B5. Participant has received immuno-suppressive therapy within 4 weeks prior to Visit 7 or is expected to receive immunosuppressive therapy during the study. Immuno-suppressive therapy is defined as administration of chronic (longer than 2 weeks) prednisone or equivalent  $\geq 0.05$  mg/kg/day within 4 weeks prior to Visit 7 (topical and inhaled steroids are allowed), radiation therapy or immunosuppressive cytotoxic drugs or monoclonal antibodies in the previous 3 years.
- B6. Participant has clinical conditions representing a contraindication to intramuscular vaccination and blood draws.
- B7. Participant is pregnant (positive urine pregnancy test at Visit 7, respectively), has plans to become pregnant at time of the enrolment to the Booster Phase (Visit 7).
- B8. Participant has a rash, dermatological condition that would, in the opinion of the Investigator, interfere with injection site reaction rating.
- B9. Participant has a known or suspected problem with alcohol or drug abuse as determined by the Investigator.
- B10. Participant has any condition that, in the opinion of the Investigator, may compromise the Participant's well-being, might interfere with evaluation of study endpoints, or would limit the Participant's ability to complete the study.
- B11. Participant is committed to an institution (by virtue of an order issued either by the judicial or the administrative authorities).
- B12. Participant has participated in another clinical study involving an investigational medicinal product (IMP) or device within 4 weeks prior to Visit 7 or is scheduled to participate in another clinical study involving an IMP, or device during the course of this study.

### **Delaying Administration of Study vaccination**

Vaccination will be delayed if:

1. Participant has current febrile illness (body temperature equal or greater  $38.0^{\circ}\text{C}$ ) or other acute illness within 48 hours prior vaccination.
2. An illness which in the judgement of the investigator may interfere with tolerability (7 days post booster) and safety assessment
3. Participant has received antipyretics within 6 hours prior to the scheduled time of vaccination.
4. Receipt of any vaccine within 30 days prior to study intervention, with the exception of the seasonal influenza vaccine. Participants will be encouraged to receive this vaccination at least 7 days before or after their study vaccine.

In addition, for a rescheduled vaccination all inclusion and none of the exclusion criteria must be met; in case not all of these criteria are met, the Participant will be excluded from further vaccination.

The rescheduled visit should be within the specified time window for the vaccination visit. In case the time window for a rescheduled first vaccination cannot be met, the Participant might be invited for a re-screening.

## STATISTICAL ANALYSIS

### Sample size justification

No formal sample size calculation has been performed. A total of 150 Participants is considered sufficient to obtain initial safety data for VLA2001, especially since inactivated vaccines are a well-established, safe vaccine technology. Fifty Participants per group will allow for 95% confidence that an AE with a true underlying incidence of about 2% would be observed in the present study.

For the Booster Phase of this study, no formal sample size calculation has been performed and no minimal or maximal number of participants is defined. Based on operational considerations the total number of participants is expected to be up to approximately 80.

### Statistical methods

**Primary safety analysis:** The number and percentage of Participants with solicited local and systemic AEs within 7 days after each and after any vaccination of the primary vaccination series (Day 1; Day 22) will be presented. Differences between treatment groups will be assessed for significance using Fisher's exact test.

**Primary immunogenicity analysis:** This will be a comparison of GMTs for SARS-CoV-2 neutralizing antibodies at 14 days after the second dose (i.e. Day 36). Geometric mean titres (GMTs) and GMT ratios will be estimated by applying an analysis of variance (ANOVA) including the factor treatment group and study site. Tukey's HSD test will be applied for pair wise comparisons.

**Secondary safety analysis:** The number and percentage of participants with unsolicited AEs, related AEs, AESIs and SAEs will be presented for each study arm, overall, by system organ class/preferred term and by severity. Differences between study groups will be assessed for significance using Fisher's exact (Fisher-Freeman-Halton) test, whereby a significant overall test will be amended by pair-wise tests, and 95% confidence interval (CI) will be presented for all AE rates.

**Secondary immunogenicity analysis:** This will include the comparison of the GMTs as well as comparison of geometric mean fold increase (GMFI) between study groups on other study days. ANOVA models will be applied as described for the primary immunogenicity endpoint. Seroconversion rates for various study days as well as rates of Participants reaching certain fold-increase will be compared between the study groups using Fisher's exact (Fisher-Freeman-Halton) test, whereby a significant overall test will be amended by pair-wise tests, and 95% CIs will be calculated.

### Data Analysis

The following data analyses will be performed:

- Part A includes safety and immunogenicity data after all participants have completed Visit 4 (Day 36).
- Part B includes safety and immunogenicity data after all Participants have completed Visit 6 (Day 208).
- An additional data analysis will be performed during part B after all Participants have completed Visit 5 (Day 106)
- Part C includes Visits 7 to 10. An analysis of Part C will be done when all participants have completed visit 9.
- Final analysis will be done when all participants have completed the last visit (Visit 10)

### **Interim/Final Report**

An interim report will be compiled based on the Visit 5 data (Day 106) and a second interim report will be compiled based on the full Part B and partial Part C (Visit 7, Visit 8 and Visit 9) data. A final study report will be published after completion of Part C (including Visit 10).

## **SAFETY ASSESSMENTS**

### **1. Unsolicited adverse events**

Unsolicited events, which include clinically relevant laboratory parameter changes and symptoms noted during symptom-driven physical examinations, need to be documented in the respective AE section of the electronic Case Report Form (eCRF) during the applicable study visit (Visits 1 to 9 or unscheduled visit(s) before Visit 9, if applicable), regardless of their source. Serious adverse events and Adverse Events of Special interest (AESIs) will continue to be documented until the end of the study. The Investigator will follow-up each AE until it is resolved or until the medical condition of the Participant is stable. Serious adverse events ongoing at the time of Visit 9 will be followed until resolution, achievement of stable clinical conditions, or until the overall end of the study at the latest. Serious adverse events that are fatal, life-threatening or suspected to be related to study treatment will continue to be reported until 6 months after the last vaccination of the respective Participant (i.e. Visit 9). The following information will be documented for each AE: severity, causality, outcome, seriousness, medically-attended, action taken to treat AE, start and stop dates.

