## **15.2 Collection, Documentation and Assessment of Adverse Events**

### **15.2.1 Unsolicited Adverse Events**

Participants will be provided and trained to use an electronic diary to make notes on unsolicited AEs up to D36 (Visit 4, see Section 15.3). Additionally, the Investigator will enquire about AEs during study visits. Clinically relevant laboratory parameter changes constitute unsolicited AEs, too, unless they are considered a symptom of an underlying AE or part of a syndrome that is reported as AE (e.g. presence of blood cells in urine in a person diagnosed

with urinary tract infection). In addition, symptoms noted during the symptom-driven physical exams (unless already covered by an AE) constitute AEs.

All unsolicited AEs need to be documented in the respective AE section of the eCRF during the applicable study visit (Visits 1 to 6 or unscheduled visit(s), if applicable), regardless of their source (AEs noted in the Participant diary [see Section 15.3], open question to Participant, laboratory parameters, symptom-driven physical examination). Serious adverse events will continue to be documented until the end of the study.

Any symptom is regarded as a separate AE. However, if the Investigator considers several symptoms to be in the context of one underlying diagnosis, the Investigator may merge these symptoms into one single appropriate AE. The AE term entered into the eCRF should contain all symptoms summarized to one event (e.g. 'Influenza with flu-like-symptoms, fever and headache').

The Investigator will follow-up each AE until it is resolved or until the medical condition of the Participant is stable. All relevant follow-up information will be reported to the Sponsor until the end of the study for each Participant. Serious adverse events ongoing at the time of Visit 8 will be followed until resolution or achievement of stable clinical conditions, latest until the overall end of the study.

**Beyond study end, SAEs that are fatal, life-threatening or suspected to be related to study treatment will be followed up to be reported until 6 months after the last study visit of the respective Participant.**

The following information will be documented for each AE: severity, causality, outcome, and seriousness, medically-attended, action taken to treat AE, action taken on IMP, start and stop dates.

Booster Phase:

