Participants taking part in the Booster Phase will use the electronic diary to collect solicited AEs and make notes on unsolicited AEs occurring until Visit 10.

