### 15.11.1 Serious Adverse Event

Any SAE should be reported via the Safety Gateway within EDC-system within 24 hours after the Investigator has become aware of the event.

Under certain circumstances the initial notification could be done by phone, but nevertheless a written SAE Report Form must be submitted to the Safety Officer within 24 hours (see Section 2).

The study centre will be provided with specific reporting procedures. SAEs will be entered into the SAE eCRF page using a recognized medical term or diagnosis that accurately reflects the event. All identified patient's documents supporting the SAE should be sent to the CRO as soon as they are requested by the Medical Monitor/Drug Safety Officer by e-mail (preferable) or by fax using the contact information on Page 3. Fatal or life-threatening SAEs that the Investigator suspects are related to the study vaccine should be telephoned to the local Medical Monitor immediately upon the Investigator's awareness of the event.

All SAEs are reported to the Sponsor for the entire study period and for 30 days after the last visit for each participant.

SAE term should represent diagnosis. Only in case no diagnosis can be identified, each symptom should be reported separately.

Medical or diagnostic procedures due to an underlying disease or symptom are not considered an AE but a consequent measure following an AE. A correct SAE report will therefore have to specify the disease or symptom as the reportable AE and the medical or diagnostic procedure as action taken.

In addition, expedited and periodic reporting to Competent Authorities and ECs will be performed in accordance with local requirements. Further reporting details can be found in the study-specific SAE procedure which is in accordance with respective EU requirements, ICH GCP, national laws and site-specific requirements. Serious adverse events that are considered as probably or possibly related and additionally are unexpected need to be reported according to the requirements for suspected unexpected serious adverse reactions (SUSARs).

Serious adverse event reports will be reviewed by the study site's physician, the Safety Officer, the study medical monitor, the Sponsor and the independent DSMB.

All AESIs will be treated as medically significant and will therefore be treated as SAEs. Thus, SAE reporting procedures are also to be applied for AESIs.

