**Beyond study end, SAEs that are fatal events, life-threatening or suspected to be related to study treatment will be followed up until 6 months after the last vaccination of the respective Participant.**

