### 22.3 Schedule of Study Procedures and Assessments for the Booster Phase

The investigator may schedule visits (unplanned visits in addition to those listed in the table, in order to conduct evaluations or assessments required to protect the well-being of the participant

Procedures/Assessments	Visit 6 Day 208 M7 (+/- 14d)	Visit 7 i Planned for mid-end September 2021 for all participants (+/- 14d)	Visit 8 14 days after booster vaccination (Visit7)  (+/- 2d)	Visit 9 28 days after booster vaccination (Visit7)  (+/- 7d)	Visit 10 Safety follow- up call 6 months after booster vaccination (Visit 7)  (+/- 14d)	Unplanned COVID- 19 Illness Visit	Ad hoc Safety Call in case of e- Diary entry (Grade 3 AE or SAE)	Visit ET
Informed consent	X							
Inclusion/Exclusion criteria check	X	X						
Delay criteria check		X						
Symptom-driven physical examination a	X	X	X	X		X		X
Prior/Concomitant medications	X	X	X	X	X	X	X	X
Vital signs b	X	X						
Urine Pregnancy test c		X						
Safety labs d [10 mL]	X	X	X	X		X		X
Immunogenicity sample e [10 mL]	X	X	X	X		X		X
Blood for PBMC Isolation f [50 mL]	X	X	X					
Saliva Sample k	X							
VACCINATION		X						
Electronic Participant Diary		E	R	R			R	R
AE/AESI/SAE Assessment	X	X	X	X	X	X	X	X

(S)AE=(serious) adverse event; AESI=adverse event of special interest; PBMC=peripheral blood mononuclear cells; R=review

- a **A symptom-driven physical examination** will be performed, i.e. only in case symptom is reported by the Participant, an assessment of the affected body system(s) will be performed.
- b **Vital signs** will include systolic and diastolic blood pressure and pulse rate while seated and at rest, and body temperature measured orally before vaccination. In addition, after an observation period of 30 minutes following vaccination pulse rate as well as blood pressure while seated and at rest will again be assessed.
- c A **urine** pregnancy test will be done prior to vaccination at Visit 7.

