- Participant with any serious unsolicited AE up to Visit 10 in the booster phase
- Participant with any AESI up to Visit 10 in the booster phase

In addition, following summaries will be presented by SOC and PT for the booster phase:

- Summary of unsolicited AEs up to Visit 9 in the booster phase
- Summary of treatment related unsolicited AEs up to Visit 9 in the booster phase
- Summary of serious unsolicited AEs up to Visit 9 in the booster phase
- Summary of AESI up to Visit 9 in the booster phase
- Summary of unsolicited AEs up to Visit 10 in the booster phase
- Summary of treatment related unsolicited AEs up to Visit 10 in the booster phase
- Summary of serious unsolicited AEs up to Visit 10 in the booster phase
- Summary of AESI up to Visit 10 in the booster phase
- Summary of unsolicited AEs by maximum severity up to Visit 9 in the booster phase

- Summary of unsolicited AEs by closest causality relationship up to Visit 9 in the booster phase
- Summary of unsolicited AEs by maximum severity up to Visit 10 in the booster phase
- Summary of unsolicited AEs by closest causality relationship up to Visit 10 in the booster phase

Adverse events that started in the booster phase will be presented separately in participant data listings.

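### The protocol gives conflicting collection windows for SAEs and unsolicited AEs (six months is equated with a 28-day visit), so the SAP's additional Visit 10 AE tables have no settled ascertainment period

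*Protocol*

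**What the plan says.** **SAEs.**

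- The synopsis has SAEs and AESIs documented to the end of the study. It then says that the fatal, life-threatening or related ones "will continue to be reported until 6 months after the last vaccination of the respective Participant (i.e. Visit 9").
- The booster schedule in Section 22.3 heads the column "Visit 9 28 days after booster vaccination (Visit7"), with a window of ±7 days. It places the six-month safety call at Visit 10 (±14 days). SAP Section 2.4 agrees on both.
- Section 15.2.1 says that, beyond study end, the same subset "will be followed up to be reported until 6 months after the last study visit of the respective Participant".
- Section 15.11.1 says that, beyond study end, the same subset "will be followed up until 6 months after the last vaccination of the respective Participant". It also states: "All SAEs are reported to the Sponsor for the entire study period and for 30 days after the last visit for each participant".
- SAEs still ongoing are carried forward from Visit 9 in the synopsis and from Visit 8 in Section 15.2.1.

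**Unsolicited AEs.**

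- The synopsis has eCRF documentation at Visits 1 to 9. Section 15.2.1 has it at "Visits 1 to 6 or unscheduled visit(s), if applicable".
- The booster paragraph of Section 15.2.1 has participants "make notes on unsolicited AEs occurring until Visit 10" in the e-Diary, and Section 15.3 says the same.
- Section 15.2.2 wants every AE up to study completion or termination in the eCRF, and Section 15.11 has all AEs reported to the end of the study.

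**Analysis.** The booster endpoints (Protocol Section 10.3.1.2, SAP Section 3.1.2) stop unsolicited and vaccine-related AEs at Visit 9 and take only SAEs and AESIs to Visit 10. SAP Section 7.2.1 has outputs to Visit 9 and also lists a "Summary of unsolicited AEs up to Visit 10 in the booster phase", with matching outputs for related AEs, severity and causality.

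**The concern.** A site cannot tell from the protocol how long to enter non-serious AEs in the booster phase, or how long to follow the gravest SAEs after the participant leaves the study. Sites relying on different sections would collect different events.

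For the analysis, a rate of unsolicited AEs to Visit 10 has a clear meaning only if every site sought such events from every boosted participant over the whole six months. If some stopped at Visit 9, the table joins full collection over the first month to partial collection over the next five, and nothing in the output would show it. Safety is a primary objective of this first-in-human study, so these windows should be unambiguous.

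**Working it through.** No formula for power or type I error is involved. The check is date arithmetic on the visit schedule, followed by setting the passages side by side.

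**Inputs**

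- Visit 8: booster + 14 ± 2 days; Visit 9: booster + 28 ± 7 days; Visit 10: booster + 6 months ± 14 days (Section 22.3).
- Six months as a calendar period: 6 × 365.25 / 12 = 182.6 days.
- Six months as the protocol itself uses it for the primary series (Section 10.1.2): Day 208 − Day 22 = 186 days.

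**1. Is Visit 9 six months after the last vaccination?**

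- Nominal gap: 182.6 − 28 = 154.6 days, or 186 − 28 = 158 days.
- Using the edges of both visit windows: from 182.6 − 14 − 35 = 133.6 days to 186 + 14 − 21 = 179 days.
- Share of six months elapsed by Visit 9: 28 / 182.6 = 15.3%, or 28 / 186 = 15.1%.
- If the last vaccination is dose 2 (no booster), the six-month visit is Visit 6.

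The synopsis equation is not reproduced under any of these readings.

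**2. Where the SAE end points fall for a boosted completer, in days after the booster**

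| Rule | Days |
|---|---|
| Documentation to end of study (Visit 10) | 182.6 to 186 |
| Six months after last vaccination (15.11.1) | 182.6 to 186 |
| Last visit + 30 days, all SAEs (15.11.1) | 212.6 to 216 |
| Six months after last study visit (15.2.1) | 365.3 to 372 |

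The second and fourth rows govern the same events (fatal, life-threatening or related, beyond study end) and differ by about six months: 365.3 − 182.6 ≈ 183 days, or 372 − 186 = 186 days. At nominal timing the second row adds no time after Visit 10, and at most 14 days if Visit 10 is held at the early edge of its window. It also ends 30 days before the general rule in the third row. For someone who terminates early, six months after vaccination can run well past the last visit.

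**3. Ongoing SAEs.** Visit 8 and Visit 9 are nominally 28 − 14 = 14 days apart.

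**4. Unsolicited AEs after the booster**

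| Source | Window |
|---|---|
| Synopsis, eCRF | Visit 9 |
| 15.2.1, eCRF | Visit 6 |
| 15.2.1 booster paragraph and 15.3, e-Diary notes | Visit 10 |
| 15.2.2, eCRF | study completion or termination |
| 15.11, reporting | end of study |
| 22.3, AE assessment marked | up to and including Visit 10 |

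Section 22.3 shows Visit 10 as a telephone call with AE assessment but no safety laboratory tests, physical examination or diary review. The synopsis counts clinically relevant laboratory changes as unsolicited AEs, and after Visit 9 no scheduled laboratory test would detect them.

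**5. SAP outputs.** The Visit 9 endpoint has its own tables (14.2.1.31, .32, .39, .40). The Visit 10 outputs for unsolicited and related AEs are additional: Tables 14.2.1.35, .36, .41 and .42, plus the Visit 10 lines that Section 7.2.1 puts in the booster overall summary (Table 14.2.1.30).

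**The case against.** The strongest reply is that this is mostly wording left over from before the booster amendment. Much of that stands.

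- A reader might infer that the gravest SAEs are collected for only 28 days. The documents do not support this. The same synopsis paragraph documents all SAEs to the end of the study, the SAE and AESI endpoints run to Visit 10, and Section 15.11.1 requires every SAE for the whole study. The visit number contradicts the duration in its own sentence and reads as a wrong cross-reference.
- A reader might count four mutually exclusive SAE end points. Documentation, reporting to the sponsor and extended follow-up of a subset are different activities and can partly coexist. What cannot stand together is Section 15.2.1 against Section 15.11.1 for the same subset, and the synopsis equation against the schedule.
- A reader might conclude that some sections allow no reporting after the last visit. No section says so, and the 30-day rule for all SAEs is unconditional.
- A reader might take the Visits 1 to 6 wording to mean that no non-serious AE is entered after the booster. It precedes the booster paragraph of that section and is probably unrevised, and the synopsis and Sections 15.2.2, 15.11 and 22.3 all call for booster-phase collection. It does, however, cover all unsolicited AEs, and the booster paragraph sets only a diary window.
- Sections 15.2.1 (booster paragraph), 15.2.2, 15.3, 15.11 and 22.3 support collection to Visit 10, so the SAP's Visit 10 tables have a basis in the protocol and need not be removed by default.

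None of this removes the Visit 9 equation, the conflict between Sections 15.2.1 and 15.11.1, or the differing eCRF windows.

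**Conclusion.** The contradictions are real, and they sit in operative safety text. The visit named in the synopsis falls about 155 to 158 days before six months. The two follow-up rules for the same post-study SAEs differ by about six months for a completer. The eCRF window for non-serious AEs is unsettled between Visit 9 and Visit 10, about five of the six booster months.

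The effect on the analysis is limited and conditional. If sites follow the synopsis, the additional Visit 10 tables could understate non-serious AEs. By how much cannot be derived from the documents, because it depends on which section sites use. The Visit 9 endpoint tables do not depend on the Visit 10 question, solicited AEs remain at seven days, and no primary endpoint, test or sample-size figure changes.

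The day counts assume nominal visit timing and a participant who completes the booster phase, with six months taken as 182.6 or 186 days. The documents do not settle which window is intended, and this point does not choose one.

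**What to change.** In the protocol:

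1. Correct the Visit 9 cross-reference in the synopsis so that the duration and the visit number agree with Section 22.3.
2. Reconcile the post-study SAE rules in Sections 15.2.1 and 15.11.1 with each other and with the 30-day rule, saying which rule governs documentation, which reporting and which follow-up.
3. Resolve Visit 8 against Visit 9 for ongoing SAEs.
4. State one collection window for unsolicited AEs, in the same words, in the synopsis and Sections 15.2.1, 15.2.2, 15.3 and 15.11, and update the Visits 1 to 6 wording.

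Then align the SAP. If non-serious AEs are collected from all boosted participants to Visit 10, keep the Visit 10 tables. If not, limit every Visit 10 output to SAEs and AESIs. That includes the Visit 10 lines of the overall summary (Table 14.2.1.30) as well as Tables 14.2.1.35, .36, .41 and .42; removing those four tables alone would leave the SAP inconsistent.

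The cost is a protocol clarification, a note to sites and, in the second case, a small edit to the SAP table list. No new visit, sample or test is needed.
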